## **1.0 PHASE II RESEARCH PLAN (PILOT RANDOMIZED CONTROL TRIAL, 3 MONTHS)**

During Phase II we will be conducting a 3-month pilot randomized control trial (RCT) of virtual diabetes self-management education and support (DSMES) with peer leaders, (adapted in Phase I), to evaluate participant recruitment and retention rates, treatment and intervention satisfaction and estimate intervention effect sizes on our primary outcomes of self-management behaviors as well as on secondary outcomes such as glycemic control (HbA1c), diabetes social support, diabetes-related distress, and adherence to gender norms. This data will be collected at baseline and three months (treatment termination. Physiological data will be collected at St Patrick Senior Center or Ypsilanti Seventh Day Adventist Church and the self-report questionnaire data will be collected telephonically or virtually. Participants will be randomized to the virtual peer leader DSMES or a control group. All virtual DSMES sessions will be held on an online platform, Zoom Med. The baseline assessment and intervention period will consist of 16 weeks. In the first 2 weeks participants will complete baseline questionnaires, interviews, and physiologic testing at St. Patrick's or Ypsilanti Seventh Day Adventist Church, telephonically, or virtually. In weeks 3 to 8 participants will be simultaneously enrolled in 6 weekly virtual diabetes self-management education (DSME) classes with a certified diabetes care and education specialist (CDCES) and two peer leaders. In weeks 9 to 14 participants will be enrolled in diabetes-self management support (DSMS) sessions with two peer leaders (no CDCES). In weeks 15 and 16 of the intervention, participants will complete the post-treatment assessment battery (See Table 1). Each group will be invited to participate in the 3-month post-intervention assessment battery. Patients who do not complete the intervention phase will also be invited to participate in the 3-month assessment battery. The physiologic testing part of the assessment will be held at Ypsilanti Seventh Day Adventist Church or St. Patrick Senior Center, a non-profit that provides comprehensive services to a diverse population of more than 2,000 seniors living throughout metropolitan Detroit. Data analyses and dissemination of study findings are anticipated to be completed in months 11-12 of the study funding period. We will also be conducting qualitative interviews to better understand the acceptability and sustainability of the intervention as routine practice in a community-based clinic.

TIMELINE	Q1			Q2			Q3			Q4		
	Dec 20	Jan 21	Feb 21	Mar 21	Apr 21	Jun 21	Jul 21	Aug 21	Sep 21	Oct 21	Nov 21	Dec 21
Study Activities												
Phase I												
Focus Group Recruitment												
Hire & Train Research Staff												
Conduct Focus Groups												
Analyze Focus Group Data												
Adapt Intervention Materials												
Intervention Recruitment												
Phase II RCT												
Randomization												
T0 Baseline Assessment												
T1 Post-Intervention Assessment												
Phase III Data Analysis												
Interviews and Focus Groups (participants and practitioners)												
Analyze and disseminate data												

**Table 1. Detailed timeline of Phase I and Phase II**

## **2.0 Background:**

Diabetes is the 6th leading cause of death in Detroit. One-third of people living in the city over the age of 50 have diabetes or pre-diabetes. Michigan's age-adjusted diabetes death rates in 2009 were 26.6 for White males, 19.1 for White females, 44.7 for Black males, and 33.6 for Black females (deaths per 100,000 population).

Diabetes is highly prevalent in Black men and they are more likely to be diagnosed with T2D compared to non-Hispanic White men. In addition, they are disproportionately more likely to have uncontrolled blood glucose levels than their non-Hispanic White counterparts.

One factor that may account for diabetes health disparities is differences in diabetes management behaviors in Black men as compared to Whites. Studies suggest that Black men in general are less likely to adhere to diabetes self-management regimens. Although studies of older Black men are more limited, those that exist suggest that they are even less likely to engage in diabetes self-management behaviors (e.g. checking blood glucose levels daily). Black men are also more likely to engage in behaviors that increase their risk for diabetes-related complications such as smoking and alcohol consumption than their non-Hispanic White peers. Black men may also face unique barriers that interfere with healthy behaviors including a lack of social support, negative patient-provider relationships, high medical fees and long work hours. While existing research clearly shows that older Black men are at elevated risk for poor diabetes management, they are also less likely to participate in interventions to improve diabetes management. Specifically, in our systematic review of T2D self-management interventions, the percentage of male participants was typically less than 15%. This is also consistent with the finding that men are more likely to drop out of diabetes self-management intervention trials.

A growing body of literature demonstrates the critical role of gender in the management of health behaviors and shows that male gender norms can conflict with both healthy behaviors and healthcare engagement. Sex refers to biological differences (e.g. chromosomes and sex organs). Gender describes the characteristics that a society or culture delineates as masculine or feminine. Among Black men specifically, the need to exhibit toughness, confidence, suppression of emotions and independence/control served as barriers to both accepting advice from care providers and accepting social support offered by family and community networks. In a recent study, Black men reported encountering significant difficulty in accepting a caring environment, such as emotional support, as this was perceived as feminized behavior, which in turn served as a barrier to seeking care. Gender-related norms among Black men also include "superman syndrome" or the ability to maintain their health without the assistance of doctors. Recommendations for gender-specific programming have included using male interventionists to reduce stigma and embarrassment related to health care seeking, improve communication with health care providers and address specific beliefs that undermine health. Peer leaders have been defined as trained lay individuals used to improve diabetes self-management in minority communities through provision of diabetes education, assistance with goal setting, problem solving, and social and emotional support. In this context, peer leaders shared cultural identity and community ties are a critical component in improving diabetes management in minorities with T2D. However, despite studies showing that interventions using peer

leader models have been successful in improving diabetes management (e.g. blood glucose monitoring) and clinical outcomes (e.g. HbA1c) among minority populations to date, these interventions have not been adapted to meet the needs of older Black men. In addition to the lack of tailoring of content or adjustment of messaging, as noted earlier, the majority of peer leaders used in these studies have been female, and in general, women are the majority of participants in diabetes intervention studies. Matching lay interventionists for the race and gender of patients may be one way to increase the likelihood that both intervention content and messaging are appropriate.

While there is a paucity of research using male peer leaders with Black men with T2D, male lay helpers have been used in other areas of health care to provide Black men with health education and support. These interventions have included prevention of chronic illness (e.g. screening for hypertension) in intervention venues such as barbershops. However, this research is limited and therefore additional work needs to be done to establish the efficacy of these approaches. In addition, as the behavioral targets of these programs were primarily health promotion and/or prevention behaviors such as increasing condom use and disease screening, and not management of a chronic disease, it is important to assess whether use of male peers as interventionists can improve health outcomes among men already living with a chronic illness. As previously noted, there is a dearth of efficacious diabetes management interventions for Black men. While the effectiveness of peer-led interventions delivering diabetes-related education and support for short-term clinical, psychosocial, and behavioral improvements is well-established, older Black men in particular are less likely to participate and are at a higher risk of drop-out from these studies. The proposed research is innovative because:

1. interventions to date have not targeted older Black men, who are at highest risk for poor diabetes health;
2. peer-led interventions have not matched peer leaders based on the gender of intervention participants nor have they;
3. tailored the intervention content utilizing the perspectives of older Black men with T2D in the adaptation process to meet the specific needs of this understudied and at-risk population.

We propose to develop training for our male peer leaders to specifically encourage conversations regarding beliefs that affect men's health and to allow modeling of alternative views and perspectives that allow for successful disease management to be framed as competence and strength. Given that the life expectancy for Black men in the US is 71, we hypothesize that targeting men in earlier stages of T2D will assist greatly in facilitating healthy aging and improving diabetes-related health outcomes later in life.

Based on our previous work, the ***long-term goal*** of our research is to determine the most effective, practical, and sustainable approach to provide diabetes self-management education and support (DSMES) to older Black men. The ***objective*** of this proposal is to examine the relative effectiveness, feasibility, and acceptability of a peer-leader intervention for Black men with T2D. To accomplish this objective, we will engage in a developmental phase and a validation phase [pilot randomized control trial (RCT)]. The RCT will be conducted with N=60 Black adult residents of metro Detroit, MI. Participants will be randomized to an enhanced usual care group or the tailored peer-leader diabetes self-management support group (PLDSMS). We ***hypothesize*** that 1)

participants in the PLDSMS group will have improved outcomes over the control group, and 2) an evaluation of measures will confirm efficacy of the intervention. Measures will be collected at baseline, 3-months and a 3-month follow-up. The primary outcome will be change in self-management behaviors measured through completion of the Perceived Diabetes Self-Management Scale and a self-report questionnaire measuring a broad range of diabetes self-management behaviors post intervention and at 3-month follow up. Secondary outcomes will be change in A1c, weight, blood pressure, quality of life, diabetes related-distress, diabetes social support, and adherence to gender norms. We **hypothesize** that 1) participants in the PLDSMS group will have improved outcomes over the control group, and that 2) participants in the PLDSMS will achieve DSMES skills at significantly higher levels than participants in the control group.

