### **3.0 Aims**

**Aim 1 (Phase 1): Refine existing intervention components from a previous peer leader trial to allow it to be best tailored to the needs of older Black men with T2D by:**

- Conducting 10 interviews with older Black/African American men with T2D.

**Aim 2: Conduct a pilot randomized controlled trial for older Black men with T2D based on what we learn from Aim 1. Development, adaptation, and refinement will involve:**

- Developing a peer led diabetes self-management education and support intervention based on our interviews and previous research.
- Conduct an open pilot study to determine feasibility and acceptability of the peer led diabetes self-management support and estimate intervention effect size on our primary outcome of diabetes self-management behaviors and changes in A1C, as well as on secondary outcomes of change in weight, blood pressure, quality of life, diabetes related-distress, diabetes social support, and adherence to gender norms. Data from the pilot trial will help refine recruitment strategies, training materials, and protocol to be used in a larger clinical study.

**Aim 3: Conduct a qualitative process evaluation of the implementation of peer led DSMS to determine feasibility and acceptability of the intervention by:**

- Recruiting 10-12 stakeholders (facilitators, participants, peer leaders, and certified diabetes care and education specialists) and complete post intervention interviews to identify barriers, perceptions and beliefs surrounding peer led DSMS targeting older Black male populations.

**Overall impact:** Data from the pilot RCT will help refine recruitment strategies, training materials, and the study protocol to be used in a larger cluster RCT. Our study will also identify strategies to increase patient participation in intervention research and improve drop out rates. This goal is in line with the mission of NIDDK to disseminate science-based information on diabetes, to improve people's health and quality of life.

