**Baseline Assessment** (Assessment Battery) All individuals that meet initial phone screening criteria and agree to participate will complete a baseline assessment. The physiological testing portion of the baseline assessment will be held in person at either St. Patrick Senior Center or Ypsilanti Seventh Day Adventist Church and the self-report questionnaire will be completed by the participant virtually or over the phone with a study team member. During the assessment the participant will be asked to complete questionnaires and interviews to determine if the participant is eligible to participate based on inclusion and exclusion criteria. Baseline assessments will last about two hours total. The PI will train all research staff in standardized data collection. Trained research staff will take biometric data of participants including height, weight, blood pressure, and A1c. Participant A1c values will be analyzed on site using a DCA Vantage Analyzer. All participants, including peer leader participants, will be paid \$20 for completing the assessment and the same assessments at T0 (baseline) and T1 (post-treatment).

**Randomization** Participants will be randomized to the peer leader diabetes self-management support (DSMS) group or a control group using a 50/50 randomization scheme. Participants will be aware if they are in the intervention group or the control group.

**Intervention (Peer Leader DSMS n=30)** Participants randomized to the peer led DSMS group will receive 6 100-minute weekly sessions of diabetes self-management education (DSME) delivered by a certified diabetes care and education specialists (CDCES) and co-facilitated by a peer leader (PL) delivered via the Zoom for Health a U-M service may be used for Protected Health Information (PHI, regulated by HIPPA). Next, participants will transition into 6 90-minute weekly PL led DSMS sessions

intentionally designed for older Black men with T2D. The CDCES will provide oversight to the PL and be available by phone if any clinical questions arise during the session.

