### **Secondary Outcome Measures**

Adherence to gender norms will be measured using the Male Role Norms Inventory-Short Form. BMI will be calculated using height and weight. Height will be measured using a stadiometer. Weight will be measured on a high quality, calibrated digital scale. BP will be measured using a digital sphygmomanometer.

Diabetes Social Support will be measured using the Diabetes Social Support Questionnaire. Diabetes-related Distress will be measured using Diabetes Distress Scale (SF-12) and lastly, a validated Diabetes Quality of Life will be used to measure quality of life. Participants will also complete questionnaires that assess socio-demographic, behavioral, psychosocial, and health services utilization and are validated in diverse populations with diabetes.

**Specific Aim 1:** Qualitative analyses will be conducted during the development phase and on the post-intervention focus groups and interviews. First, we will develop codes utilizing a grounded theory approach and will start with the formulation of categories and definitions developed directly from the text. Content from transcripts will be coded for themes and patterns. Through this process a coding manual and definitions will be finalized. The refined manual will be used to guide ongoing coding and pairs of coders will read subsequent transcripts keeping codes that achieve 80% agreement on code application. Analyses will be conducted using Dedoose. This data will be used to conduct a final refinement of treatment content as needed.

**Specific Aim 2:** The proposed study includes a sample size of 64 Black men, 30 in the intervention arm, 30 in the control arm and 4 trained as peer leaders for the intervention arm. We will assess the impact of the intervention on diabetes management and HbA1c (primary outcomes) and on secondary outcomes using multilevel modeling, with intervention group as a between-subjects factor (2 levels) and time as a within subjects factor (3 levels). HbA1c, diabetes self-management, and social support at baseline, 3 and 6 months will be used as the dependent variables. Independent variables include intervention group, time of assessment, and interaction between time and intervention

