group. Random effects will be allowed for the intercept (to allow differences in baseline measurements) and the slope (to allow differences in the trajectories of change). Covariates e.g. length of time since diabetes diagnosis, age will be tested as predictors of the outcome and retained if significant at  $p < .10$ .

**Power Analysis:** Assuming 20% attrition, we expect a final sample size of 48, approximately 12 per group (with 2 groups in the treatment arm). If we assume correlations of 0.25 between successive measurements of HbA1c, then this sample size will yield power of 0.8 to detect a difference of 0.6 standard deviation between average values of HbA1c in treatment and control groups.

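### Section 2.0 says the pilot will confirm efficacy while sections 1.0 and 3.0 set it up to estimate effect sizes, and the design gives only limited support for a confirmatory claim

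*Combined protocol and SAP*

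**What the plan says.** Section 2.0 (Background) gives two hypotheses in confirmatory terms: that "an evaluation of measures will confirm efficacy of the intervention" and that "participants in the PLDSMS will achieve DSMES skills at significantly higher levels than participants in the control group". It names self-management as the primary outcome and lists A1c among the secondary outcomes.

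Section 1.0 gives a different purpose: to evaluate recruitment, retention and satisfaction and to "estimate intervention effect sizes on our primary outcomes of self-management behaviors". Aim 2 in section 3.0 agrees. It covers feasibility and acceptability and aims to "estimate intervention effect size on our primary outcome of diabetes self-management behaviors and changes in A1C", with the data used to refine a larger trial.

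Section 7.0 (Specific Aim 2) has "30 in the intervention arm, 30 in the control arm and 4 trained as peer leaders for the intervention arm". It treats diabetes management and HbA1c as joint primary outcomes in a multilevel model with three time points and random intercepts and slopes. Its Power Analysis assumes 20% attrition, 48 completers and a correlation of 0.25 between successive HbA1c measurements, and states power of 0.8 for a 0.6 SD difference in HbA1c. It states no alpha and no power for self-management.

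**The concern.** A pilot meant to estimate an effect and a trial meant to confirm one lead to different conclusions from the same data. If the section 2.0 wording is carried into the report, a p-value above 0.05 may be read as a failed intervention and one below 0.05 as proven efficacy. Section 3.0 says the results will shape a larger cluster trial, so either misreading could affect how that trial is planned.

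A confirmatory claim also needs things fixed in advance that the plan does not fix: one agreed primary outcome, an alpha, a rule for multiple outcomes, one visit schedule, and an analysis that respects group delivery.

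**Working it through.** **Inputs.** 30 randomised per arm and 20% attrition (section 7.0) give 60 × 0.8 = 48 completers, or 24 per arm. The correlation r = 0.25 is stated for HbA1c only. Alpha is not stated; two-sided 5% is assumed. Effects are in SDs of a single measurement.

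**Number of visits.** Section 1.0 and section 5.0 (Baseline Assessment, Follow-Ups) give baseline and one post-treatment assessment. Section 2.0 and Specific Aim 2 in section 7.0 add a later one. Both schedules are worked below.

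**Reproducing the plan's 0.80.** Take the mean of two post-baseline visits, adjusted for baseline, with equal correlations:
- Effective SD = √[(1 + 0.25)/2 − 0.25²] = √0.5625 = 0.750
- SE = 0.750 × √(2/24) = 0.217
- Power at 0.6 SD: 0.6/0.217 = 2.77, less 1.96 gives 0.81, so 0.791 (normal) or 0.774 (noncentral t)
- 95% half-width = 2.013 × 0.217 = 0.44 SD

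The stated figure is therefore roughly reproduced when two post-baseline visits are used.

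**One post-treatment visit, adjusted for baseline.**
- Effective SD = √(1 − 0.25²) = 0.968
- SE = 0.968 × √(2/24) = 0.280
- Power at 0.6 SD = 0.574 (normal) or 0.556 (noncentral t), so a true 0.6 SD effect is missed about 44% of the time
- 95% half-width = 0.563 SD

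Without baseline adjustment, power is 0.547. No two-sided comparison at the single visit reaches 0.80.

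| | One post visit | Two post visits |
|---|---|---|
| 95% CI half-width | 0.56 SD | 0.44 SD |
| Power at 0.6 SD | 0.56 to 0.57 | 0.77 to 0.79 |
| Difference detectable with 80% power | 0.78 SD | 0.61 SD |

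**What a non-significant result leaves open.** With an estimate of exactly zero, the upper limit equals the half-width: 0.56 or 0.44 SD. With an estimate just short of significance it is about twice that: 1.13 or 0.87 SD. Conversely, an observed 0.6 SD at one visit gives an interval of 0.04 to 1.16 SD.

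**Larger and smaller effects, one visit, clustering ignored.** Power is about 0.19 at 0.3 SD and 0.79 to 0.82 at 0.8 SD.

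**Self-management.** The plan gives no correlation for this outcome. Assumed values of 0.5 and 0.7 in the one-visit formula give half-widths of 0.50 and 0.42 SD, with power at 0.6 SD of 0.65 and 0.81.

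**Session groups.** Section 5.0 has group sessions in both arms. The Power Analysis describes "approximately 12 per group (with 2 groups in the treatment arm"), which puts two groups in treatment; groups of 12 in control are an inference from 48/12 = 4. The model has no session-group term. The plan gives no ICC; 0.01 to 0.05 is assumed.
- Design effect = 1 + 11 × ICC = 1.11 to 1.55
- True two-sided error of a nominal 5% test that ignores it = 2 × [1 − Φ(1.96/√design effect)] = 6% to 12%

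**Multiplicity.** If self-management and HbA1c are each tested at 5%, the chance of at least one false positive is 1 − 0.95² = 0.0975 if the two are independent.

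**The case against.** The strongest reply is that section 2.0 states hypotheses and sets no decision rule. Its labelled objective is to examine relative effectiveness, feasibility and acceptability, and a directional hypothesis can sit beside effect-size estimation. Section 7.0 also claims 80% power for 0.6 SD, and that claim roughly reproduces under the three-assessment schedule that section 2.0 itself gives. Both points stand. They limit how far the criticism goes, but they leave unchanged the wording about confirming efficacy, the missing alpha and the lack of any power statement for self-management.

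Three stronger readings are tempting and should not be drawn:
- **That 24 per arm can support no confirmatory conclusion in either direction.** This is too absolute. With independent participants, a test at a preset alpha keeps its error rate at this size, and an effect near 0.8 SD has about 80% power even at one visit.
- **That four session groups leave 2 degrees of freedom and a half-width near 1.5 SD.** That figure needs a single assumed ICC of 0.05 and a number of control groups that the plan does not state. The choice of 2 degrees of freedom drives most of it: at an ICC of zero the same method already gives 4.303 × 0.280 = 1.20 SD.
- **That a go/no-go decision rests on the p-value.** The documents contain no such rule. Section 3.0 says the data will refine recruitment strategies, training materials and the protocol.

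**Conclusion.** The conflict of purpose is real and should be corrected. Sections 1.0 and 3.0 describe estimation for a larger trial; section 2.0 promises confirmation of efficacy and significance.

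The design gives limited support for that promise. For HbA1c, the half-width is about 0.56 SD and power at 0.6 SD about 0.56 with one post-treatment visit, or about 0.44 SD and 0.77 to 0.79 with two post-baseline visits. A non-significant result would not exclude a moderate effect. A significant one would carry an error rate of about 6% to 12% if session groups are correlated to the assumed degree and the analysis ignores it. For self-management, the primary outcome in section 2.0, the plan gives neither power nor a correlation.

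These figures rest on 24 completers per arm, an assumed two-sided 5% level, the HbA1c correlation of 0.25 (0.5 to 0.7 assumed for self-management), and an assumed ICC of 0.01 to 0.05 in groups of 12 in both arms. They do not show that the trial is uninformative or that a large effect would go undetected.

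**What to change.** 1. In section 2.0, replace the hypotheses with an estimation objective: *to estimate the between-arm difference in self-management and HbA1c change with 95% CI, to plan the larger trial*. State that p-values are exploratory and neither confirm nor refute efficacy.
2. In section 7.0, Specific Aim 2, make estimates with confidence intervals the main output. Report any session-group ICC descriptively only, with its interval, which will be wide with so few groups.
3. In section 7.0, Power Analysis, present the figure as expected precision, or as power for HbA1c only, with alpha stated and under the visit schedule actually collected. Without this step the 80% power claim would conflict with the new objective.

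If the sponsor prefers to keep a confirmatory test, sections 2.0, 3.0, 5.0 and 7.0 must instead be reconciled on primary outcome, alpha, multiplicity, visits and clustering.

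The first route changes wording only and adds no participants or visits. Its cost is that the trial gives up a confirmatory efficacy claim.

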**Follow-Ups** The follow up assessment for both the peer led DSMS group and control group will occur at three months (post-treatment assessment). All participants, including peer leader participants, will return to the St. Patrick's Senior Center or to Ypsilanti Seventh Day Adventist Church for physiological testing and complete the self-report questionnaire telephonically, or virtually. The same measurements and surveys will be completed. Participants will be compensated \$20 for completing this assessment. Data will be stored in REDCap, a secure, web-based application hosted at UM.

**Maintenance of Samples** Strategies will be used to encourage attendance of group sessions and to complete follow up interviews. Reminder emails, texts and/or calls will be sent before each session to remind participants by the study team. In addition, the study team will collect participant contact information from baseline to

follow up phase. The study team will also ask participants to provide additional contact person(s) that the study team can contact if they cannot reach the participant.

**Participant Retention** The following procedures will be used to minimize participant attrition: 1) Data collection sessions will be completed at the Senior Center site or the Ypsilanti Seventh Day Adventist Church in order to maximize the convenience of data collection for subjects, and 2) multiple techniques are used to increase the likelihood that participants will keep their data collection appointments, including advanced scheduling, multiple reminder letters, and phone reminders. Participants who withdraw will still be asked to participate in study data.

**Data Collection & Data Safety** For Phase II (intervention), data will be collected through the following methods: finger stick capillary blood samples, blood pressure measurements, weight, height, exit interviews regarding treatment satisfaction, surveys, audio recorded interviews and treatment sessions, and transcribed interviews and treatment session recordings. Data that are obtained specifically for research purposes will be collected only with informed consent. All data will be collected over the course of the award period.

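### The plan promises and models three assessment waves but dates only two; on two visits the time factor has an empty level and the stated power of 0.8 falls to about 0.57

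*Combined protocol and SAP*

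**What the plan says.** **Three waves.** Section 2.0 states "Measures will be collected at baseline, 3-months and a 3-month follow-up" and sets the primary outcome as change in "diabetes self-management behaviors post intervention and at 3-month follow up". Section 7.0, Specific Aim 2, specifies "time as a within subjects factor (3 levels" and continues: "HbA1c, diabetes self-management, and social support at baseline, 3 and 6 months will be used as the dependent variables". The same paragraph adds: "Random effects will be allowed for the intercept (to allow differences in baseline measurements) and the slope (to allow differences in the trajectories of change".

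**Two waves.** Section 1.0 says "This data will be collected at baseline and three months (treatment termination"; it ends the support sessions in week 14 and puts the post-treatment battery in weeks 15 and 16. Section 5.0, Baseline Assessment, pays participants for "the same assessments at T0 (baseline) and T1 (post-treatment". Section 5.0, Follow-Ups, says "The follow up assessment for both the peer led DSMS group and control group will occur at three months (post-treatment assessment" and describes no later visit. The assessment rows of Table 1 are T0 and T1 only.

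**Unclear.** After placing the post-treatment battery in weeks 15 and 16, Section 1.0 invites each group to a battery labelled as three months post-intervention. Its next sentence shortens the label to a 3-month battery, the timing used elsewhere for the end of treatment. Section 10.0 lists baseline, post-treatment and follow-up assessments without dates.

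**Power.** The Power Analysis paragraph in Section 7.0 assumes 20% attrition, a final sample of 48 and a correlation of 0.25 between successive HbA1c measurements. It claims power 0.8 for a 0.6 SD difference in average HbA1c.

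**The concern.** The mention of 6 months in Section 7.0 means that the follow-up in Section 2.0 cannot simply be the end-of-treatment visit under another name. Staff who work from Section 5.0 would nevertheless collect nothing quantitative after T1.

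Three things are at stake. The later time point of the primary outcome has no dated visit behind it. The analysis model is written for data that the schedule does not produce. The power statement may rest on a measurement that is not taken. A wave that is not collected cannot be recovered at the analysis stage, so this has to be settled before the visits take place.

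**Working it through.** **Inputs.** Section 7.0 gives 30 per arm, 20% attrition, correlation r = 0.25 and a difference of 0.6 SD. Final sample: 60 × 0.8 = 48, or n = 24 per arm. Alpha is not stated, so two-sided 0.05 is assumed. Equal correlation between all waves (compound symmetry) is also assumed, with no allowance for clustering within session groups.

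**Formulas, in SD units.** SE = √(2f/n), where f is the variance factor of the analysis. Power = Φ(0.6/SE − 1.96). Detectable difference at 80% power = (1.960 + 0.842) × SE.

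**The plan's own figure.** For the mean of two post-baseline waves adjusted for baseline, f = (1 + r)/2 − r² = 0.625 − 0.0625 = 0.5625. Then SE = √(2 × 0.5625/24) = 0.2165, and power = Φ(2.771 − 1.96) = 0.791, close to the stated 0.8.

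**The scheduled visits.** For T1 adjusted for T0, f = 1 − r² = 0.9375. Then SE = √(2 × 0.9375/24) = 0.2795, and power = Φ(2.147 − 1.96) = 0.574.

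| Analysis | f | Power for 0.6 SD | Detectable SD |
|---|---|---|---|
| Two post-baseline waves, baseline-adjusted | 0.5625 | 0.791 | 0.607 |
| Mean of all three waves | (1 + 2r)/3 = 0.5 | 0.836 | 0.572 |
| T1, baseline-adjusted | 0.9375 | 0.574 | 0.783 |
| T1 alone | 1 | 0.547 | 0.809 |
| Change from T0 to T1 | 2(1 − r) = 1.5 | 0.396 | 0.991 |
| Mean of T0 and T1 | (1 + r)/2 = 0.625 | 0.748 | 0.639 |

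The last row is generous. Randomisation should leave no difference at T0, so a 0.6 SD difference at T1 is only (0 + 0.6)/2 = 0.3 SD in that mean.

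**Sensitivity.**
- With the noncentral t distribution, 0.791 becomes 0.774 and 0.574 becomes 0.556.
- If correlation decays with distance between waves (AR1), the adjusted three-wave figure is 0.765.
- A three-wave change score (mean of the two later waves minus baseline) gives 0.500, so not every three-wave analysis reaches 0.8.
- At one-sided 0.05, the two-visit figures are 0.692 (adjusted), 0.668 (T1 alone) and 0.521 (change). Only the mean of T0 and T1 then passes 0.8, at 0.837.

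**Identifiability on two visits.** Code time 0 and 1, with intercept variance a, slope variance b, their covariance c and residual variance s:
- Var(T0) = a + s
- Cov(T0, T1) = a + c
- Var(T1) = a + 2c + b + s

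This gives three equations in four unknowns (rank 3 of 4), so the model is not identified if c is free. If c = 0, then a = Cov, s = Var(T0) − Cov and b = Var(T1) − Var(T0), which is identified with nothing to spare. Three waves give 6 distinct elements and rank 4, so all four parameters are identified.

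**The case against.** The strongest reply is that a later assessment may be intended. Section 10.0 names one, and the three-month post-intervention battery in Section 1.0 can be read as one. This stands to the extent that a reader should not infer that no later visit is mentioned anywhere, or that half of the primary outcome will certainly go uncollected. The visit is undated, unpaid in Section 5.0, absent from the Table 1 rows and contradicted by Follow-Ups. That is a conflict to resolve and does not prove an omission.

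It can also be said that the model does not fail outright. This is right in part. Section 7.0 does not say whether the intercept and slope may covary, and with independent effects the model is just identified. Even with a free covariance, the group-by-time effect remains estimable. The empty third level of time remains a problem in either case.

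A third reply is that this is a pilot for feasibility and effect sizes, and that Sections 1.0, 3.0 and 7.0 name the primary outcomes without a follow-up time. That lowers the weight of the power figure. However, Section 2.0 states superiority hypotheses and Section 7.0 makes a power claim, so both need to match the schedule.

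Three further inferences are tempting but unsupported:
- **Weeks 15–16 are the last contact with participants.** Section 3.0 and Table 1 plan interviews with participants after the intervention.
- **Sustainability in the plan means a lasting effect.** Section 2.0 uses the idea for the way the programme is provided, and Section 1.0 for routine practice in a community-based clinic.
- **The award period leaves no room for a 6-month visit.** The month shading of Table 1 is not available in the text reviewed, so this cannot be checked either way.

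**Conclusion.** The number and dates of assessments contradict each other in current text, and the plan must be corrected. On the two visits actually scheduled, the 3-level time factor cannot be used, the random-effects structure is at best just identified, and nothing can be estimated about the effect after support ends.

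Power for 0.6 SD is about 0.57 baseline-adjusted, with 0.40 to 0.75 across the other two-visit analyses, against 0.79 when two post-baseline waves are counted. The baseline-adjusted detectable difference is about 0.78 SD instead of 0.61 SD. These sizes rest on two-sided alpha 0.05, compound symmetry, r = 0.25, 24 per arm and no clustering. The plan does not show its power formula, so the match at 0.79 is a reconstruction. The contradiction itself depends on none of these assumptions.

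**What to change.** Decide which schedule is meant and make every section agree.

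**If two visits are meant:**
- Remove the later follow-up from Sections 2.0 and 10.0, and state in Section 1.0 that the three-month battery is T1.
- In Section 7.0, set time to two levels (T0, T1) and drop 6 months from the dependent variables.
- Replace the random intercept and slope with an unstructured 2×2 covariance (3 parameters for 3 elements) or a baseline-adjusted ANCOVA.
- Limit conclusions to the end-of-treatment effect.
- Restate power with its alpha and formula: about 0.57 for 0.6 SD, or 80% for about 0.78 SD, under the assumptions above.

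This changes text only. The price is giving up the follow-up claim and stating a less favourable power. Keeping 80% for 0.6 SD would instead need 41 per arm, or 82/0.8 = 102.5, about 103 enrolled.

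**If the 6-month wave is meant:** enter a dated T2 in Section 1.0, Table 1 and Section 5.0 (Baseline Assessment and Follow-Ups), with its payment. The 3-level model can then stand, and the stated power is roughly supported at 0.79. The cost is one further assessment round, with its payments, staff time and added calendar time.
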